10.4 Compliance with Study Registration and Results Posting Requirements

Not applicable.

10.5 Quality Management System

By signing this protocol, the Sponsor agrees to be responsible for implementing and maintaining a quality management system with written development procedures and functional area standard operating procedures (SOPs) to ensure that studies are conducted and data are generated,

documented, and reported in compliance with the protocol, accepted standards of Good Pharmacoepidemiology Practice, and all applicable federal, state, and local laws, rules and regulations relating to the conduct of the study.

1. METHODOLOGY

1.1 Introduction and Purpose

The purpose of this statistical analysis plan (SAP) is to describe the final analysis of the data of the study.

The documents used in preparation of this SAP are:

- Study Protocol Version 4.0, dated 10 September 2019.
- Study annotated CRF Version 2.0, dated 17 May 2019.

1.2 Objectives and Endpoints Mentioned in the Protocol

1.2.1 Study Objectives

The primary objective of this study is to investigate the relation between patient, tumor and site characteristics and systemic treatment choices of stage IV untreated non-small cell lung cancer (NSCLC).

It is hypothesized that there is a relation between the systemic treatment choice and several explanatory variables that can be categorized as follows:

- Patient demography characteristics
- Medical history
- Co-morbidities
- Autoimmune disease
- Current/recent medication
- Prior cancer treatment in earlier stage
- Site characteristics

A detailed list of the variables can be found in the Section 1.5. For each of the variables, it will be queried whether the variable had an (important) impact on the systemic treatment choice.

1.2.2 Endpoints

The outcome variable is systemic treatment choice or best supportive care, defined as:

1. Chemotherapy (chemo)
2. Immunotherapy (IO)
3. Immuno combined therapies (IO+IO)
4. IO+chemo
5. IO+bevacizumab+chemo (IO+bev+chemo)
6. Best supportive care (BSC)

In practice, only four categories of the outcome variable were observed: Chemo, IO, IO+chemo, and BSC. Therefore, in the analysis the outcome variable will be considered as having four levels.

1.3 Study Design

This is a multicenter non-interventional cross-sectional study on first-line systemic treatment choice in stage IV NSCLC patients coming to the consultation. The study was to involve approximately 21 Belgian hospitals where consecutive patients with metastatic stage IV NSCLC selected for systemic

treatment or BSC are included in the trial at the time the patient signs the informed consent form (ICF). Patients selected for systemic treatment, should have received at least their first dose and a maximum of one cycle of the same treatment.

The pneumo-oncologist who treats the patient fills in the CRF, indicating the systemic treatment or BSC option and the link with the variables that impact the choice of systemic treatment or BSC. The actual value of the considered variables is also recorded in the CRF.

A questionnaire must be filled in characterizing the site and allowing the site to be assigned to a group based on the number of newly diagnosed patients per year with lung cancer (diagnostic volume) and whether the site participates in interventional clinical trials (CT participation).

In order to minimize bias, it was emphasized to the participating centers that consecutive patients need to be included in the study. In addition, a maximum of 10% (20 patients) of the total study population can be enrolled per site.

1.4 Sample Size Justification

No formal sample size calculation was performed. The protocol states that a maximum of 210 eligible patients and a minimum of 200 patients are to be included to have a representative picture of the pneumo-oncologists' NSCLC systemic treatment decision in Belgium.

1.5 Recorded Data

This section describes the covariates, that are considered in the analysis. These are divided into Site characteristics, recorded at the level of the site, and Patient characteristics, recorded at the level of a patient.

1.5.1 Site Characteristics

The following main site characteristics are recorded and will be used to classify the sites into four groups:

- Approximate number of newly diagnosed NSCLC patients (all stages) in reference year 2018 (diagnostic volume)
- Participation in lung cancer interventional clinical trials (CT participation) (yes/no)

The following additional site characteristics are recorded:

- Genetic testing
 - In-house (yes/no)
 - Referral testing (yes/no)
- PD-L1 IHC
 - In-house (yes/no)
 - Referral testing (yes/no)
- NGS testing
 - In-house (yes/no), if yes: type (whole exome/tumor gene panel/foundationONE/unknown¹)
 - Referral testing (yes/no), if yes: type (whole exome/tumor gene panel/foundationONE/unknown¹)

¹ Considered missing in the analysis

1.5.2 Patient Characteristics

After making the treatment choice, the investigator records the following variables and indicates whether the characteristic impacted the treatment choice (yes/no). Of the variables indicated as having an impact, the investigator chooses at least one and a maximum of three most important characteristics.

Demographic data

- Age (years)
- Gender (male/female)
- Weight loss (%)
- Smoking status (current/former (≥ 1 year)/never/unknown¹)
- ECOG status (0/1/2/3-4/unknown¹)
- Patients' preference for treatment choice (yes/no/unknown¹)

Medical history

- Metastatic disease status (M1a/M1b/M1c/unknown¹)
- Tumor burden:
 - Tumor size diameter (mm)
 - Number of metastatic sites
- Brainmets (yes/no), if yes:
 - Symptomatic/asymptomatic
 - Treated with SRT/treated with WBRT/not treated
- Livermets (present/not present/unknown¹)
- Concomitant malignancies (present/not present/unknown¹)
- Histology (squamous/non-squamous/not otherwise specified¹)
- IHC PD-L1 (PD-L1 TPS $< 1\%$ / $1-49\%$ / $\geq 50\%$ / unknown¹)
- High TMB (≥ 10 mutations/Mb) (present/not present/unknown¹)
- Genetic testing complications (turnaround time/biopsy availability/not tested¹/not applicable¹)

Co-morbidities

Presence (yes/no) of the following diseases:

- Myocardial infarction in the last year
- Congestive heart failure
- Peripheral vascular disease
- Hypertension
- Cerebrovascular event in the last year
- Transient ischemic attack in the last year
- Diabetes with complications
- Renal disease
- Liver disease
- Hematological disease
- Chronic obstructive pulmonary disease
- Chronic infections
- Mental disorders

¹ Considered missing in the analysis

Autoimmune disease

Presence, and in case present, active (yes/no), of the following diseases:

- Inflammatory interstitial lung disease
- Inflammatory bowel disease (IBD)
- Inflammatory joint disease
- Psoriasis
- Connective tissue disease

Current/recent medication

- Corticosteroids (yes/no), and if yes, low dose/high dose (≥ 10 mg/day Prednisolone or equivalent)
- Other immunosuppressants
- Antibiotics

Prior cancer treatment in earlier stage NSCLC

Did the patient undergo the following treatment (yes/no) and if yes, the year of the treatment:

- Single-modality treatment
- Multi-modality treatment
- Surgery/radiotherapy
- Previous IO treatment

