3 METHODOLOGY

3.1 Summary of Study Design

This is a multicenter non-interventional cross-sectional study in stage IV NSCLC patients on first-line systemic treatment coming to the consultation.

Consecutive patients with metastatic stage IV NSCLC selected for systemic treatment or best supportive care will be included in the trial at the time the patient signed the informed consent form (ICF). Patients that were selected for systemic treatment, should have received at least their first dose and a maximum of one cycle of the same treatment.

The pneumo-oncologist that treats the patient will fill in the CRF, indicating the systemic treatment option and the link with the variable categories that impacted positively or negatively the systemic treatment option. The actual value of variables linked to a variable category will also be recorded in the CRF.

A questionnaire has to be filled in characterizing the site and allowing the site to be assigned to a group based on the number of newly diagnosed patients per year with lung cancer and whether the site participates in interventional clinical trials. All sites will be retrospectively divided in four groups; high number of patients per year (more than median NSCLC patients per year) and participating in interventional clinical trials, high number of patients but not participating in interventional clinical trials, low number of patients (less than median NSCLC patients per year) and participating in interventional clinical trials or low number of patients and not participating in interventional clinical trials.

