3.3 Inclusion Criteria

All inclusion and exclusion criteria will be reviewed by the investigator or qualified designee to ensure that the subject qualifies for the study.

In order to be eligible for participation in this trial, the subject must:

- Have voluntarily agreed to participate by giving written informed consent/assent for the trial.

- Have a histologically or cytologically confirmed diagnosis of stage IV NSCLC on first-line (1L) systemic treatment.
- Have received at least their first dose of the selected systemic treatment and a maximum of 1 cycle of the same treatment. Patients that were selected to receive best supportive care will not have to comply to this inclusion criterion.
- Be ≥ 18 years of age on day of signing informed consent.

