4.2 Covariates

The actual values of the following covariates will be recorded within the eCRF, which can be discrete or continuous in nature. In addition to the actual values, the investigator will also have to indicate whether the covariates had an impact on the treatment choice in a binary fashion.

✓ Patient demography characteristics at study entry:

- Age
- Gender:
 - F
 - M
- Weight loss
 - (%)
- Smoking status:
 - Current
 - Former (≥ 1 year)
 - Never
 - Not known
- ECOG status:
 - 0
 - 1
 - 2
 - 3-4
- Patient's preference
 - Yes
 - No

✓ Medical history:

- Metastatic disease stage:
 - M1a
 - M1b

- M1c
- Tumor Burden:
 - Tumor size
 - Number of metastatic sites
- Brainmets:
 - No
 - Symptomatic
 - Asymptomatic
 - Treated with SRT
 - Treated with WBRT
- Livermets
 - Present
 - Not present
- Concomitant malignancies
 - Present
- Histology:
 - Squamous
 - Nonsquamous
 - NOS
- IHC PD-L1:
 - PD-L1 TPS <1%,
 - PD-L1 TPS 1 - 49%
 - PD-L1 TPS ≥50%
- High TMB (≥ 10 mutations/Mb (Cfr. CHECKMATE-227))
 - Present
 - Not present
- Testing
 - Turn-around-time
 - Not tested
 - Biopsy availability
 - Type of NGS testing (e.g. whole exome, gene panel, platform, ...)

- ✓ Comorbidities
 - Myocardial infarction in the last year
 - Congestive heart failure
 - Peripheral vascular disease
 - Hypertension
 - Cerebrovascular event in the last year
 - Transient ischemic attack in the last year
 - Diabetes without complications
 - Renal disease
 - Liver disease
 - Hematological disease
 - Chronic obstructive pulmonary disease
 - Chronic infections
 - Mental disorders

- ✓ Autoimmune disease
 - Active inflammatory interstitial lung disease
 - Non-active inflammatory interstitial lung disease
 - Active inflammatory bowel disease (IBD)
 - Non-active IBD
 - Active inflammatory joint disease
 - Non-active inflammatory joint disease
 - Active psoriasis
 - Non-active psoriasis
 - Active connective tissue disease
 - Non-active connective tissue disease

- ✓ Current/recent medication
 - Low dose corticosteroids
 - High dose (≥ 10 mg/day Prednisolone or eq) corticosteroids
 - Other immunosuppressants (i.e. Anti-TNF- α , MMF, ...)
 - Antibiotics

- ✓ Prior cancer treatment in earlier stage NSCLC
 - Single Modality treatment
 - Multi-Modality treatment
 - Surgery / radiotherapy
 - Previous IO treatment
 - Year of treatment

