For each variable category, the physician has to determine whether it had an impact on his/her treatment decision, yes or no. For all variable categories, for whom the answer was yes, the physician has to select the three most important variable categories that impacted his treatment decision.

5 Study Flow Chart

	V1	V2*
Informed consent	X	
Inclusion	X	
Exclusion	X	
Systemic treatment option		X
Variable categories impacting treatment choice		X
Patient demography characteristics		X
Medical history		X
Co-morbidities		X
Autoimmune disease		X
Baseline medications		X
Prior cancer treatment in earlier stage		X
Site characteristics		X

*time of V2 and V1 can coincide. V2 will only be created if V1 is successfully passed.

It is allowed that information is collected retrospectively.

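### PD-L1 (and TMB) is not defined as the result available at the treatment decision and 'unknown' is set to missing, so later results may enter the analysis and choices made without a result are not analysed as a group

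*SAP*

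**What the plan says.** **Time of recording.** SAP 1.5.2 places recording after the choice: "After making the treatment choice, the investigator records the following variables". Under protocol 3.3 a patient on systemic treatment must "Have received at least their first dose of the selected systemic treatment and a maximum of 1 cycle of the same treatment"; patients on best supportive care (BSC) are exempt. The note under the flow chart in protocol section 5 adds: "It is allowed that information is collected retrospectively". It gives no cut-off at the decision date.

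**Time the value refers to.** Protocol 4.2 attaches one time anchor to its covariate list, "Patient demography characteristics at study entry". It belongs to demography. PD-L1 and TMB stand under medical history, which has none.

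**PD-L1 levels.** SAP 1.5.2 lists TPS <1%, 1-49%, ≥50% and unknown, and a footnote makes unknown missing. TMB is treated the same way. No report date and no pending level is listed for either.

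**Delay.** Protocol 4.2 lists "Turn-around-time" under a general testing heading. The SAP carries it as one level of an item on genetic testing complications.

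**Use.** SAP 2.3 tabulates PD-L1 by treatment choice. SAP 2.4 tabulates the investigator's rating of each variable's impact by treatment choice. SAP 2.5 offers the PD-L1 category to an exploratory stepwise multinomial model, subject to the rule in SAP 1.8.2 that fewer than 20% of values are missing or unknown.

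**The concern.** The study asks which characteristics lie behind the first-line choice, and protocol 1.1 names PD-L1 expression among the bases of that choice. A characteristic can act on a decision only in the state in which the physician knew it. Suppose a patient starts chemotherapy while PD-L1 is pending and a TPS ≥50% is reported before the form is completed. Nothing in the documents prevents that patient from being entered as TPS ≥50% on chemotherapy, which reads as a choice made despite high expression.

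A patient whose result never arrives is entered as unknown and becomes missing. Yet having no result can itself shape the choice, and choices made without one are the kind of treatment issue or data gap that protocol 1.2 sets out to find. At stake are a diluted association for a key biomarker and the loss of a group that the study wants to see.

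**Working it through.** The plan gives no figure that bears on this point, since there is no sample size or power calculation. The check is therefore a reading of the text plus three small calculations.

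**1. Can a late result enter?** Recording follows the choice, entry of treated patients follows the first dose, and retrospective collection is allowed. The only time anchor does not cover PD-L1, and for treated patients study entry is itself later than the decision. So a late result can be entered, and the listed fields do not allow an analyst to recognise it.

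**2. Illustrative size at TPS ≥50%.** All inputs are assumptions; none is in the documents.
- Chemotherapy alone in 5% if the result is known and 40% if it is pending.
- Share pending at the decision q = 5%, 10% or 20%, with every pending result later returned and entered.
- 30% to 35% of 210 patients with TPS ≥50%, that is 63 to 74.

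Apparent rate = (1 − q) × 0.05 + q × 0.40. Share attributable to lateness = q × (0.40 − 0.05) / apparent rate.

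| q | Apparent rate | Attributable share | Excess patients of 63 to 74 |
|---|---|---|---|
| 5% | 0.0475 + 0.020 = 6.8% | 0.0175 / 0.0675 = 26% | 1.1 to 1.3 |
| 10% | 0.045 + 0.040 = 8.5% | 0.035 / 0.085 = 41% | 2.2 to 2.6 |
| 20% | 0.040 + 0.080 = 12.0% | 0.070 / 0.120 = 58% | 4.4 to 5.2 |

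**3. Direction and size of the dilution.** Again by assumption, the probability of immunotherapy alone is 0.75 if TPS ≥50% is known, 0.05 if TPS <50% is known, and u = 0.05 or 0.15 if no result is available, whatever the later category. With a share f of late results, each recorded category has probability (1 − f) × known value + f × u, so the difference between categories is 0.70 × (1 − f).

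| f | Difference | Odds ratio (u = 0.05; u = 0.15) |
|---|---|---|
| 0 | 0.70 | 57; 57 |
| 5% | 0.665 | 48; 44 |
| 10% | 0.63 | 40; 35 |
| 20% | 0.56 | 30; 23 |
| 30% | 0.49 | 22; 15 |

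Late results unrelated to the choice weaken the association; they do not create one.

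**4. Would recoding late results to the existing unknown level be enough?** No. The rule in SAP 1.8.2 requires fewer than 20% missing or unknown. Since 0.20 × 200 = 40 and 0.20 × 210 = 42, PD-L1 stays eligible with at most 39 of 200 or 41 of 210 unknown and is dropped at 40 or 42. Below that limit, the SAP does not say how the model handles missing covariates. Under complete-case fitting, patients without a PD-L1 result leave the model.

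**The case against.** A reader might infer that PD-L1 is recorded whenever it becomes available, and that late results are analysed as drivers of the choice. The documents do not say so. The sentence in SAP 1.5.2 dates the data entry, not the result, and retrospective collection fits equally well with abstracting what was known at the decision. Field instructions belong to the annotated CRF cited in SAP 1.1, which is not among the documents. That part of the objection stands.

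The study also has a partial safeguard. The investigator states for each variable whether it affected the choice, so a late PD-L1 result can be marked as having no impact. SAP 2.4 rests on that answer and is less exposed, and the regression is only exploratory. But no impact covers both a result that was known and set aside and a result that was not there. SAP 2.4 tabulates the answer by treatment, not by PD-L1 level or availability, and the tables in SAP 2.3 do not use it.

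Delay is partly captured by the turnaround item, so it would be wrong to say that it appears nowhere or would be reported as physician preference. The item is a weak substitute. SAP 1.5.1 lists genetic testing separately from PD-L1 IHC, so the item need not cover PD-L1. Its not-tested and not-applicable levels are missing, so under the 20% rule it reaches the model only if more than 80% of patients have one of the two remaining levels.

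Two further points stand. The other medical history items lack an anchor too; PD-L1 and TMB matter more here because they depend on a laboratory turnaround. And at 5% to 10% late results the illustrated association remains very strong.

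**Conclusion.** The point holds as a gap in definition with a concrete consequence. The documents do not tie PD-L1 or TMB to the decision, the listed fields do not allow timing to be recovered, and the stated rule turns having no result into missing data. Results returned after the choice may therefore enter SAP 2.3 and 2.5, and patients decided without a result are not analysed as a group.

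The actual size is unknown, because the documents give no frequency of late results. The apparent rates of 6.8%, 8.5% and 12.0% against 5%, and the attributable shares of 26%, 41% and 58%, rest wholly on the assumptions listed, including that every pending result returns and is entered. It is tempting to count every chemotherapy-alone patient with a pending result as due to lateness, which would give q × 0.40 / rate = 30%, 47% and 67%. That overstates it, because by the same assumptions 5% of those patients would have had chemotherapy alone with the result known. The weakening of the association also depends on late results being unrelated to the choice.

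**What to change.** 1. Check the annotated CRF for a PD-L1 or TMB report date, or an instruction on which result counts. If it already ties the value to the decision, cite it in the SAP and the first half of the point falls away.
2. In SAP 1.5.2, 2.3 and 2.5, stop treating PD-L1 'unknown' as missing and analyse it as its own level. Amend the 20% rule in SAP 1.8.2 to match, because it counts unknown values.
3. Define the recorded PD-L1 and TMB category as the result available at the decision.
4. Report pending and not tested separately where the data allow. Not testing may follow from a BSC decision, in which case it is a consequence of the outcome.
5. If a report date exists, add a sensitivity analysis that reclassifies results dated after the first dose or BSC decision as not available. State that first dose is only a proxy: a result arriving between decision and first dose would still count as available.

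**Cost.** Steps 2 and 3 are SAP wording, plus one parameter per outcome contrast, that is 3 with four outcome levels. SAP 1.2.2 already reports which outcomes were observed, so a new CRF level may come too late, and the definition in step 3 may not be verifiable for data already entered; the report should say so. Collecting dates from about 21 sites would be a larger task, so the sensitivity analysis is proposed only if dates are already held.

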1.6 Definitions and Derived Variables

Site type

Sites will be divided into four groups based on the two main site characteristics, diagnostic volume and CT participation:

- High number of patients per year (more than the median number of NSCLC patients per year) and participating in interventional clinical trials
- High number of patients and not participating in interventional clinical trials
- Low number of patients (less than or equal to the median number of NSCLC patients per year) and participating in interventional clinical trials
- Low number of patients and not participating in interventional clinical trials

1.7 Analysis Set

The following analysis set is considered:

Eligible Population (EP): All subjects enrolled in the study, who have given informed consent and who satisfied all inclusion and none of the exclusion criteria.

The patients that should be excluded from the EP will be discussed during a data review meeting.

All analyses will be performed on the EP.

1.8 General Methodology

The statistical analysis will be performed using the SAS software for WINDOWS, Version 9.2. It will consist of a descriptive analysis and statistical modelling. Furthermore, lists of individual data will be provided for all patient characteristics.

1.8.1 Descriptive Analysis

Throughout this document the following terminology is used for indicating the type of descriptive analysis:

- 'Descriptive statistics' is the description to be provided for quantitative variables, and consists of the mean, standard deviation (SD), 95% confidence interval (CI) on the mean, minimum, 1st quartile, median, 3rd quartile, maximum, number of available observations, and number of missing observations.
- 'Frequency distribution' is the description to be provided for ordinal and nominal variables and consists of numbers and percentages for each of the scores or categories. Exact 95% CIs will be provided for key variables.

The descriptive analysis consists of:

1. Site Characteristics

Descriptive statistics will be provided for the diagnostic volume. Other site characteristics, including the site type, will be described by frequency distributions.

2. Patient Characteristics by Outcome Variable and by Site Type

Descriptive statistics and frequency distributions will be used to describe numerical and ordinal/nominal patient characteristics, respectively. The analysis will be performed for:

- All patients in the EP
- By outcome variable (Chemo+IO, Chemo, IO, BSC)
- By site type (4 subgroups).

Also, frequency distributions of the outcome variable will be given for all patients in the EP and by site type.

3. Impact of Covariates on the Outcome Variable

The impact of variables, as indicated by the investigator, on the outcome variable, is described as one of the following:

- Important impact (variable selected as one of the three most important characteristics)
- Impact (variable indicated as having an impact, but not selected among the three most important characteristics)
- No impact (variable not indicated as having impacted the treatment choice)

For each variable the frequency distribution of the impact is provided per level of the outcome variable (chemo, IO, IO+chemo, and BSC).

